13 ANALYSIS POPULATION

- **The full analysis set (FAS) population** consists of all patients included in the study after selection criteria review, patients who meet all selection criteria. The CRF contains the screening criteria information in the form of a binary variable (Yes/No) for each item described. The full analysis set will be used for all descriptive analysis.
- **The clinical benefit population** consists of patients who have available data that allow the primary efficacy endpoint assessment. The clinical benefit population will be used for primary objective (see primary objective section).
- **The safety population** includes all adult patients in whom CHIMAERA™ has been used. It includes all patients who have undergone an intramedullary nailing technique with the CHIMAERA™ medical device. The safety analysis will be performed in the “safety population” which includes all patients who have undergone an intramedullary nailing technique with the CHIMAERA™ medical device.

A list of patients belonging to each of the populations will be sent to the sponsor for confirmation prior to analysis.

14 STATISTICAL ANALYSIS METHODS

The methods of analysis to be used for both objectives of the study and for description of the study variables are detailed below.

Quantitative variables will be described with measures of central tendency and dispersion: mean, median, SD (standard deviation), Q1 (first quartile) and Q3 (third quartile), minimum and maximum. Qualitative variables will be described using absolute and relative frequencies.

In the descriptive analysis of qualitative variables, two percentage columns will be presented, total percentage (%) and valid percentage (% valid), that are respectively, the percentage over the sum of valid responses plus missing values and the percentage over the total of valid responses.

Clopper-Pearson confidence intervals will be shown at 95.0%.

No imputation for missing data will be considered.

Data will be analysed using SPSS v29.0 or later

Interim Analysis: During the study development and if the sponsor considers it necessary, an interim analysis could be performed after at least 22 subjects will be enrolled and completed the treatment in which bone union has been achieved within 12 months from the nail implant in order to preliminary confirm the results obtained.

No adjustment for multiple comparisons will be performed.

15 DESCRIPTIVE STATISTICAL ANALYSIS

15.1 PATIENT DISPOSITION

A summary of patients included in the study, as well as those who are in each populations and the reasons for not belonging to one of the populations will be shown.

16 SCREENING VISIT

16.1 DEMOGRAPHIC DATA

This analysis will be performed on FAS population.

The descriptive statistic (Mean, SD, Median, Q₁, Q₃, Min, Max) will be shown for the following continuous variables:

- Age at surgery (calculated as date of surgery minus date of birth)
- Age at ICF signature (calculated as date of ICF signature minus date of birth)
- Height
- Weight
- BMI

The categorical variables to be described are, N and (%):

- Gender (Male / Female)
- Race (Caucasian, African, Asian , Other (a list will be shown))

16.2 ANAMNESIS

This analysis will be performed on FAS population.

The categorical variables to be described are, N and (%):

- Did the patient work at the time of surgery? YES / NO
- Was the patient a smoker? YES / NO, If “YES”, descriptive statistic (Mean, SD, Median, Q₁, Q₃, Min, Max) of the number of cigarettes per day will be shown
- Did the patient drink alcoholic beverages? YES / NO, If “YES”, the frequency will be shown:
 - Occasionally
 - During meals
 - Several times a day even outside meals
- Comorbidities:

- Osteoporosis
- Diabetes
- Tumor
- Other (a list will be shown)
- Does the patient take medication regularly? YES / NO, If "YES", type and dosage will be shown.

16.3 CLINICAL DIAGNOSIS

This analysis will be performed on FAS population.

The descriptive statistic (Mean, SD, Median, Q₁, Q₃, Min, Max) will be shown for the following continuous variable:

- Time from date of trauma (calculated as date of ICF signature minus date of trauma)

The categorical variables to be described are, N and (%):

- Clinical diagnosis (Non pathological fracture / Non-union)
- Classification of Fracture (31A / 31B / 31C)
 - If select 31A, Choose one of these subgroups will be described: 31A 1.1 / 31A 1.2 / 31A 1.3 / 31A 2.2 / 31A 2.3 / 31A 3.1 / 31A 3.2 / 31A 3.3
- Was there a second fracture in the femoral shaft extending distally to a point approximately 10cm proximal to the intercondylar notch? YES / NO, If "YES" Choose one of these subgroups will be described: 32A, 32B, 32C:
 - If selected 32A, Choose one of these subgroups will be described: 32A1 / 32A2 32A3
 - If selected 32B, Choose one of these subgroups will be described 32B2 / 32B3
 - If selected 32C, Choose one of these subgroups will be described: 32C2 / 32C3
- Which is the cause of the fracture? (Trauma / Other)
 - If trauma will be described: High energy Low energy Info not available / Other (a list will be shown)
- Are RX (AP + ML) related to diagnosis available? YES / NO

17 SURGERY VISIT

This analysis will be performed on FAS population.

The categorical variables to be described are, N and (%):

- Treated Femur (Left / Right)
- Distal diameter of the nail (10 mm / 11mm)
- CCD angle (125° / 130°)
- Length of the nail (280 mm / 300 mm / 320 mm / 340 mm / 360 mm / 380 mm / 400 mm / 420 mm / 440 mm / 460 mm)
- The main proximal lag screw is sliding or fixed? (Sliding / Fixed)
- Was the additional (optional) proximal screw also applied? YES / NO
- Was the nail distally locked? YES / NO, If "YES", a static or dynamic locking or a secondary dynamization? will be described (Static / Dynamic / Secondary Dynamization)
- In addition to the nail, were additional synthetic media applied? YES / NO, If "YES", the additional method used will be described

The descriptive statistic (Mean, SD, Median, Q₁, Q₃, Min, Max) will be shown for the following continuous variable:

- Duration of the surgery skin to skin (hours)

The categorical variables to be described are, N and (%):

- Has the patient been transfused? YES / NO, If "YES", descriptive statistic (Mean, SD, Median, Q₁, Q₃, Min, Max) of the number of used blood bags will be shown
- Are intraoperative fluoroscopies (AP + ML) or, preferably, RX (AP + ML) available in the short post-operative period related to the final nail placement? YES / NO

The descriptive statistic (Mean, SD, Median, Q₁, Q₃, Min, Max) will be shown for the following continuous variables:

- Xap (mm)
- Dap (mm)
- Xlat (mm)
- Dlat (mm)
- TAD (mm)

18 DISCHARGE VISIT

This analysis will be performed on FAS population.

The descriptive statistic (Mean, SD, Median, Q₁, Q₃, Min, Max) will be shown for the following continuous variable:

- Time from surgery to Discharge (days) (calculated as Date of discharge minus date of surgery)

The categorical variable to be described is, N and (%):

- Time from surgery to Discharge (days) within the time windows estimated in the protocol (1-20 days)? (Yes / No)

The categorical variable to be described is, N and (%):

- Was any medication prescribed to the patient due to the surgery? YES / NO, If “YES” will be described:
 - Antibiotic
 - Anti-inflammatory
 - Analgesic
 - Heparin
 - Other (A list will be shown)
- Did the patient refer any info related to pain at the site of nail application? YES / Data not available), If “YES” will be described:
 - No pain
 - Pain

19 FIRST FOLLOW UP VISIT (1 MONTH)

This analysis will be performed on FAS population.

The descriptive statistic (Mean, SD, Median, Q₁, Q₃, Min, Max) will be shown for the following continuous variable:

- Time from surgery to first follow up visit (months) (calculated as Date of first follow up minus date of surgery)

The categorical variable to be described is, N and (%):

- Time from surgery to first follow up visit (months) within the time windows estimated in the protocol (1-3 months)? (Yes / No)

The categorical variables to be described are, N and (%):

- Was the patient examined on an outpatient basis or contacted by telephone because he was unable to reach your hospital? (Outpatient visit / Telephone contact)
- Have the medications the patient takes regularly changed? YES / NO, If "YES", type and dosage will be shown.
- Did the patient refer any info related to pain at the site of nail application? YES / Data not available), If "YES" will be described:
 - No pain
 - Pain
- Are follow up fluoroscopies (AP + ML) or, preferably, RX (AP + ML) available? YES / NO

The descriptive statistic (Mean, SD, Median, Q₁, Q₃, Min, Max) will be shown for the following continuous variables:

- Xap (mm)
- Dap (mm)
- Xlat (mm)
- Dlat (mm)
- TAD (mm)

The categorical variables to be described are, N and (%):

- Observer 1: According to medical opinion, is/are the fracture/s treated with Chimaera nail consolidated? YES / NO, If "NO", motivate will be described
- Observer 2: According to medical opinion, is/are the fracture/s treated with Chimaera nail consolidated? YES / NO, If "NO", motivate will be described.

- Number of patients in which consolidation has been achieved according to the two observers.

20 SECOND FOLLOW UP VISIT (6 MONTHS)

This analysis will be performed on FAS population.

The descriptive statistic (Mean, SD, Median, Q₁, Q₃, Min, Max) will be shown for the following continuous variable:

- Time from surgery to second follow up visit (months) (calculated as Date of second follow up minus date of surgery)

The categorical variable to be described is, N and (%):

- Time from surgery to second follow up visit (months) within the time windows estimated in the protocol (3-9 months)? (Yes / No)

The categorical variables to be described are, N and (%):

- Was the patient examined on an outpatient basis or contacted by telephone because he was unable to reach your hospital? (Outpatient visit / Telephone contact)
- Have the medications the patient takes regularly changed? YES / NO, If "YES", type and dosage will be shown.
- Did the patient refer any info related to pain at the site of nail application? YES / Data not available), If "YES" will be described:
 - No pain
 - Pain

21 THIRD FOLLOW UP VISIT (12 MONTHS)

This analysis will be performed on FAS population.

The descriptive statistic (Mean, SD, Median, Q₁, Q₃, Min, Max) will be shown for the following continuous variable:

- Time from surgery to third follow up visit (days) (calculated as Date of third follow up minus date of surgery)

The categorical variable to be described is, N and (%):

- Time from surgery to third follow up visit (months) within the time windows estimated in the protocol (9-15 months)? (Yes / No)

The categorical variables to be described are, N and (%):

- Was the patient examined on an outpatient basis or contacted by telephone because he was unable to reach your hospital? (Outpatient visit / Telephone contact)
- Have the medications the patient takes regularly changed? YES / NO, If "YES", type and dosage will be shown.
- Did the patient refer any info related to pain at the site of nail application? YES / Data not available), If "YES" will be described:
 - No pain
 - Pain
- During the year did the patient come back to work? (YES / NO / At time of surgery the patient didn't work at all / Data not available)
- Are follow up fluoroscopies (AP + ML) or, preferably, RX (AP + ML) available? YES / NO

The descriptive statistic (Mean, SD, Median, Q₁, Q₃, Min, Max) will be shown for the following continuous variables:

- Xap (mm)
- Dap (mm)
- Xlat (mm)
- Dlat (mm)
- TAD (mm)

The categorical variables to be described are, N and (%):

- Observer 1: According to medical opinion, is/are the fracture/s treated with Chimaera nail consolidated? YES / NO, If "NO", motivate will be described
- Observer 2: According to medical opinion, is/are the fracture/s treated with Chimaera nail consolidated? YES / NO, If "NO", motivate will be described.

- Number of patients in which consolidation has been achieved according to the two observers.

22 DISCONTINUATION VISIT

This analysis will be performed on FAS population.

The categorical variable to be described is, N and (%):

- Reason the patient was discontinued

23 PRIMARY OBJECTIVE

Primary objective: the primary objective of this study is to evaluate the clinical benefit of the long variant of the CHIMAERA™ used in adult patients according to the IFU in routine clinical practice from the time of surgery within 12 months follow-up after nail implant.

This analysis will be performed on the clinical benefit population.

The clinical benefit analysis will be performed in those patients who meet the following criteria:

- Patient has achieved bone union at the 12 months follow-up visit and this is the only evaluation available.
- Patient has achieved bone union at first follow-up this being the only evaluation available.
- Patient has both bone union evaluations completed (first follow up visit and last follow up visit) and achieved bony union at the end of the follow-up period. (considered a responder)
- Patient underwent reoperation but the reason for this was secondary dynamization. *If it will be indicated 'secondary dynamization' in ADDITIONAL SURGERY the patient will be included in this analyses (all other no).*
- Patient with fractures on the upper limbs not caused by the CHIMAERATM (e.g. simply stumbled or had a car accident) . *ADVERSE EVENTS section, answer "Unanticipated/Other adverse event (specify below)" specifying that an upper limb fractures occurred, but is "not related" to Chimaera (question "According to medical opinion, is the Adverse Event related to Chimaera?") (if it is collected any upper limbs fractures "related" to Chimaera in the question "unanticipated/Other adverse event", the patient will not be included in the analyses (not belong to clinical benefit population).*
- Patient underwent reoperation after first bone union evaluation. FU visit 1 or 3: the observer 1 and observer 2 certify that the bone union has been assessed. *Those patients in which the answers where "YES" and subsequently underwent a reoperation in ADDITIONAL SURGERY will be included (excluded the option "secondary dynamization").*
- Patient who has not suffered contralateral leg fracture. *EXCLUSION CRITERIA "Has the patient been diagnosed with bilateral proximal femur fractures? YES / NO" should be "NO".*
- Patient in whom no refraction occurred where the nail was applied. *This is to be found in ADVERSE EVENT (if it is marked 'bone fracture' the patient will not be included in this analyses).*

The categorical variable to be described is, N and (%) and Clopper-Pearson confidence intervals will be shown at 95.0% as well:

- Number of patients that reached consolidation according to the two observer's opinion in at least one visit (visit 1 or visit 3). Only if both evaluations are positive in each visit, the treatment goal will be considered achieved.

The descriptive statistic (Mean, SD, Median, Q₁, Q₃, Min, Max) will be shown for the following continuous variable:

- Time to consolidation from surgery (months), considered at the first visit in which the answer is “Yes” in “According to medical opinion, is/are the fracture/s treated with Chimaera nail consolidated?” variables in both observers. Calculated as date of first date of consolidation minus date of surgery.

A list with consolidation variables will be shown.

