PRIMARY EFFICACY ENDPOINTS	
The clinical benefit of CHIMAERA™ will be assessed by the percentage of patients in which bone union has been achieved within 12 months from the nail implant.
 
The clinical benefit analysis will be performed in those patients who meet the following criteria:
 
 - Patient has achieved bone union at the 12 months follow-up visit and this is the only evaluation available. - Patient has achieved bone union at first follow-up this being the only evaluation available. - Patient has both bone union evaluations (first follow up visit and last follow up visit) completed and achieved bone union at the end of the follow-up period. (considered a responder) - Patient underwent reoperation but the reason for this was secondary dynamization. - Patient with fractures on the upper limbs not caused by the CHIMAERA™ (e.g. simply stumbled or had a car accident) - Patient underwent reoperation after first bone union evaluation. - Patient who has not suffered contralateral leg fracture. - Patient in whom no refracture occurred where the nail was applied. 
A double evaluation will be required (observer 1 and observer 2). Only if both evaluations are positive, the treatment goal will be considered achieved.

SECONDARY TOLERABILITY / SAFETY ENDPOINTS	
The safety profile of CHIMAERA™ will be assessed through the percentage of patients that required a reoperation (i.e., additional surgery) caused by at least one of the following safety events:

	
 - Expected or unexpected adverse effect potentially or certainly related to the CHIMAERA™ (Adverse Device Effects (ADEs)/Serious Adverse Device Effects (SADEs)) since the nail application until 6 months follow-up after nail implant. - Medical Device Deficiency (MDDs) (i.e., breaking, loosening, or bending of the nail or of the screws) that caused an effect on the patient since the nail application until 6 months follow-up after nail implant. 
All the reoperations that have occurred are considered but also those that have not occurred but that could have occurred (e.g., a patient who had a cut out but for any reasons has not been operated). It should be considered also all ADE/SADE/MDD that could have caused an additional operation.
																								

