13. STATISTICS

13.1 Statistical and Analytical Plans

Prior to any statistical analysis, a statistical analysis plan (SAP) shall be prepared and approved, which shall provide the technical details of the statistical analysis described below. Any deviation from the SAP shall be described and justified in the final study report.

All patients meeting the screening criteria will be included in the analysis, a list will be given of the patients removed from the analysis, as well as the reason for their removal. A general description of the variables included in the study will be provided. The distributions of absolute and relative frequencies for qualitative variables will be presented, as well as mean, standard deviation (SD), median, minimum and maximum for quantitative variables. If considered appropriate, 95% confidence intervals will also be presented. No imputation for missing data will be considered.

Analysis will be performed using IBM SPSS Vs 22.0. When an inferential analysis is required, parametric tests will be used for continuous variables and nonparametric tests in the case of ordinal or categorical or nonparametric variables. All hypothesis tests will be two-sided and with a significance level of 0.05. For variables not fitting a normal (or parametric) distribution, the Mann-Whitney test (for unpaired data) and the Wilcoxon test (paired data) will be used. Contingency tables and the comparison of proportions and/or frequency distributions will be analyzed using the chi-square test (or Fischer's exact test when appropriate) will be used.

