13.1.1 Population(s) of analysis

The full analysis set (FAS) population consists of all patients included in the study after selection criteria review. The full analysis set will be used for all raw data listings.

The clinical benefit population consists of patients who have available data that allow the primary efficacy endpoint assessment.

The safety population includes all adult patients in whom CHIMAERA™ has been used.

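### The eight-item list for the primary analysis conflicts with the available-data population, has no combining rule, and on its workable readings makes the denominator depend on outcome

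*SAP*

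**What the plan says.** Two rules govern who enters the primary analysis.

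- **Available data.** Protocol 13.1.1: "The clinical benefit population consists of patients who have available data that allow the primary efficacy endpoint assessment". SAP 13 says the same ("consists of patients who have available data that allow the primary efficacy endpoint assessment") and assigns this population to the primary objective. The result of the evaluation plays no part.
- **Eight items.** Protocol 5 and 13.1.2.1 state: "The clinical benefit analysis will be performed in those patients who meet the following criteria". SAP 23 names the clinical benefit population, repeats the list and adds notes to items 4 to 8.

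Items 1-3 cover a 12-month evaluation only, a first follow-up evaluation only, and both evaluations. Each requires union. Item 1 reads "Patient has achieved bone union at the 12 months follow-up visit and this is the only evaluation available". Item 3 ends "achieved bony union at the end of the follow-up period. (considered a responder", which is the language of an outcome rule.

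The SAP notes then act on individual patients:

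- Item 4: with a secondary dynamization, "the patient will be included in this analyses (all other no".
- Item 5: a patient with a device-related upper-limb fracture does "not belong to clinical benefit population".
- Item 6: a patient reoperated for another reason enters if both observers had already certified union.
- Item 7: the contralateral-fracture item is checked through the exclusion criterion on bilateral proximal femur fractures.
- Item 8: a patient with an adverse event marked as bone fracture is left out.

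No and/or is stated. SAP 23 then counts a patient as achieved if both observers are positive at visit 1 or visit 3.

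**The concern.** A patient with both evaluations completed and no union has the data that SAP 13 asks for, yet meets none of items 1-3. A patient reoperated before union is assessable too, but the notes leave that patient out. In both cases entry depends on how the patient fared, while the estimate is meant to describe how patients fared.

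The union rate and its Clopper-Pearson interval are the sole primary result, and Protocol 6.2 gives confirming the benefit/risk ratio as the study's purpose. Without a combining rule, two analysts could also use different denominators on the same data.

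**Working it through.** **1. Readings of the list**

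- *All items required.* Items 1 and 2 each require their own evaluation to be the only one available, so they exclude each other. Nobody qualifies.
- *Any item suffices.* Item 7, as noted, only repeats exclusion criterion 3 of SAP 12. Every eligible patient meets it, so the removal notes do nothing.
- *Items 1-3 as entry conditions, plus the notes.* Assessed non-unions leave, except any who enter through item 4 or 5.
- *Notes only.* Non-unions with no reoperation or fracture stay. Reoperations other than dynamization without prior certified union leave, as do patients marked with a bone fracture.

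**2. Enumeration of patient types**

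Take visits 1 and 3 as positive, negative or unavailable (not both unavailable). Take reoperation as none, dynamization, other before union or other after union, and bone fracture as yes or no. After impossible combinations are dropped, 52 types remain: 34 responders and 18 non-responders under the SAP 23 numerator.

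- Items 1-3 as strict entry conditions, plus the notes on items 4, 6 and 8: 12 responder types and 0 non-responder types are kept.
- Notes on items 4, 6 and 8 only: 15 of 34 responder types and 6 of 18 non-responder types are kept.

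These are counts of types, not of patients. Of the 18 non-responder types, 6 have only a negative visit 1, so their 12-month status is unknown.

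**3. Inputs for size**

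N = 44, literature union rate 98.3% with lower limit 93%, and the Clopper-Pearson 95% interval (SAP 9 and 14). The documents give no failure count, so counts are assumed. N = 44 is taken as given. An exact interval of total width at most 0.10 reproduces five of the seven sample-size rows, but it gives 36, not 44, at 99.9%. Nothing here depends on that row.

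- Expected non-unions: 44 × 0.017 = 0.75, and 44 × 0.07 = 3.08.
- Chance of at least one: 1 − 0.983^44 = 0.53, and 1 − 0.93^44 = 0.96.

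**4. Effect on the estimate**

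Removing k failures changes x/n to x/(n − k), which is always upward.

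| Assumed failures | Removed | Rate (95% CI) |
|---|---|---|
| 1 | 0 | 43/44 = 97.7% (88.0-99.9) |
| 1 | 1 | 43/43 = 100% (91.8-100) |
| 3 | 0 | 41/44 = 93.2% (81.3-98.6) |
| 3 | 1 | 41/43 = 95.3% (84.2-99.4) |
| 3 | 2 | 41/42 = 97.6% (87.4-99.9) |
| 3 | 3 | 41/41 = 100% (91.4-100) |

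If r of the k patients removed are responders, the rate becomes (x − r)/(n − k). This exceeds x/n only when r/k is below x/n. With 3 failures, removing one responder and no failure gives 40/43 = 93.0%, slightly below 93.2%.

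As a scale for the notes-only reading, the cited average rate of reoperation due to device effects is 5.9% (range 0.0-27.5%). That gives 44 × 0.059 = 2.6 patients (range 0 to 12.1). Not all of these would be reoperated before certified union, so the number removed could be smaller.

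**The case against.** A reader might infer that the plan yields 100% by construction. The documents do not support that as the only reading. Items 1-3 carry no notes, and if only the notes are applied, plain non-unions stay in. The 100% result needs items 1-3 to act as entry conditions and item 7 to be disregarded.

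A reader might also infer that everyone removed counts against the rate. Some are responders under SAP 23: union at visit 1 followed by refracture, or reoperation before union with union at visit 3. With items 1-3 as entry conditions, union at visit 1 but not at visit 3 also leaves.

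Other points on the plan's side:

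- Protocol 13.1 says "All patients meeting the screening criteria will be included in the analysis", but the same sentence foresees a list of removed patients with reasons. It is weak evidence of contradiction. The conflict rests on Protocol 13.1.1 and SAP 13 against SAP 23.
- The notes on items 4 and 6 need not contradict each other. Item 4 can govern dynamization, and item 6 other reoperations after certified union. The text should say so.
- Failures are not hidden. SAP 15.1 gives reasons for not belonging to a population, SAP 19 and 21 report two-observer union in the full analysis set, and SAP 24 reports additional surgery and adverse events.
- A lone negative at visit 1 (window 1-3 months) does not settle union within 12 months. Leaving such patients out of the known results is defensible.
- At 98.3% there is a 47% chance of no non-union in 44.

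All of this stands and limits the size of the claim. None of it supplies a combining rule or makes entry independent of outcome.

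**Conclusion.** Wrong as written. The two definitions of the primary population conflict, and neither literal reading (all items, or any item) gives the list a workable effect. Both readings that give the notes effect select patients partly on outcome.

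The size depends on the reading and on failure counts that the documents do not give. With items 1-3 as entry conditions, the rate goes to or near 100%: up by 2.3 points with 1 failure in 44 and by 6.8 points with 3. With the notes only, the shift is partial (2.1 points if 1 of 3 failures is removed). It is upward when the patients removed have a lower union rate than those kept. With no failures it is zero.

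The analysis is descriptive and has no success threshold, so the harm is a shifted or irreproducible estimate, not a wrongly passed test. Confidence is high for the contradiction and lower for any particular size of shift.

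**What to change.** In Protocol 5 and 13.1.2.1 and in SAP 23:

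1. Use one denominator that does not select on union, reoperation or fracture. This is the population of Protocol 13.1.1 and SAP 13, spelled out as full-analysis-set patients whose two-observer data allow the 12-month endpoint to be assessed.
2. Move items 1-3 to the responder rule in SAP 23. Settle how a patient positive at visit 1 and negative at visit 3 is classified, because item 3 and the at-least-one-visit rule differ there.
3. Delete the notes that remove patients for reoperation, refracture or device-related fracture.
4. State in advance one analysis rule for a reoperation or nail-site refracture before recorded union, and clarify how the notes on items 4 and 6 fit together.
5. Do not count a patient whose only evaluation is negative at visit 1 as a known 12-month failure. Report these patients as undetermined in the SAP 15.1 disposition table. Show the rate with them excluded and, as a sensitivity analysis, with them counted as not achieved.

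Optionally, reword the interim trigger (Protocol 13.4.2, SAP 14) so that it counts patients evaluable for the endpoint whatever their union result.

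The cost is protocol and SAP wording; no new data are needed. The reported rate may be less favourable.
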